The **Opioid Addiction Recovery Support (OARS)** software, a solution provided by Q2i (a company based in Boston, MA), is designed to improve clinical management of patients receiving MAT for OUD using a dashboard that shows real-time measurement of patient achievements in their recovery progress. The software also provides opportunities for patients to interact with their clinical providers. As such, patients may be better connected to and supported by the healthcare team throughout their recovery. This extended connection and support may foster clarity and adherence to treatment plans,

better retention in treatment, and a corresponding reduction in negative treatment outcomes such as relapse and overdose.

OARS is designed to be used as a standalone solution or integrated into an existing EHR. At the center of OARS is a software program, MATRA, that uses artificial intelligence to analyze information from the EHR and from patients to provide an early and accurate relapse risk assessment for patients receiving MAT for OUD. The MATRA system determines risk factors and generates risk estimates by mining and correlating past data and results (i.e., what past patients did and whether they relapsed), allowing for earlier risk detection and consideration of a variety of subtle factors. The system continues learning from real-time data, including how well results fit the known models. The resulting MATRA score is used by clinicians as a factor for considering early interventions and case management decisions to prevent lapse or relapse. The advantage of MATRA and its use of artificial intelligence is that it continuously mines data used to refine risk scores that are used to inform treatment decisions. Data used by MATRA in the continuous learning algorithms include the patient's attendance and levels of engagement in treatment, an electronic "journal" that patients use several times per week to self-report mood (levels), ongoing responses to their treatment, the frequency and extent of use of educational and motivational materials available to patients in OARS, and results of urine drug tests. An algorithm compiles these various types and formats of data, with training to predict future outcomes using real-time data. The algorithm continues to learn and refine predictions using training and validation datasets, which is consistently improving accuracy for predicting treatment outcomes, particularly drug relapse.

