Concurrently with baseline data collection, study staff will also work with clinics to initiate the OARS platform according to the determined start date. Clinics will begin using the OARS platform with all MAT patients seen at that time. Therefore, patients receiving TAU when the OARS platform is implemented will shift care to using OARS. Patient care and treatment of OUD will then commence under the OARS condition for a period of eight months for each clinic. To compare outcomes under the OARS condition to those that occurred under TAU, comparable data will be directly collected through the OARS platform. Additionally, patient-level data collected during the OARS condition will be used to assess to what extent different levels of provider and patient engagement with OARS relate to opioid abstinence among patients. Data elements of interest (patient demographics, medications, and billing information) that are not transmitted through OARS will be obtained from each clinic's EHR and delivered directly to Q2i through secure file transfer.

All patient-level data will be collected via the EHR and transmitted to Q2i study staff via a secure file transfer system. Patients' medical record identifier will be included in each of the data transmissions to link data across TAU and OARS conditions. No one outside of the Q2i engineer will have access to patient identifiers across both conditions. Patients will not be required to submit any data for the purpose of this research. Providers will be interviewed by UCLA study staff. Interviews will be transcribed and the transcripts will be de-identified prior to sharing with Q2i staff.

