6.3 Data Analysis

Data will be collected pre and post integration of the OARS platform within the EHRs of six clinics. The primary analyses will focus on examining outcomes from the index visit versus 6 months post implementation of OARS. The analyses will assess the effect of OARS on study outcomes. The primary predictor of interest will be the OARS intervention compared to TAU. Descriptive and repeated measure analyses will be conducted to test the hypotheses that OARS condition will result in increased number of patients treated with MAT, increased retention, and increased opioid abstinence compared to TAU. We will consider several clinic-level factors potentially associated with the study outcome, including clinic size, duration of the clinics' MAT program, and ancillary clinic services.

The secondary analysis will use data from patients treated after OARS implementation. A logistic regression model will be employed to estimate effect of provider and patient engagement with the OARS platform (number of days of OARS engagement, number of interactive features used) on patient opioid abstinence (opioid-negative urine toxicology). We will adjust for patient-level covariates including demographic variables (age, gender, race/ethnicity, level of education), other substance use, severity of opioid use, and medical comorbidities.

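### The secondary analysis does not place OARS engagement before the urine test or adjust for earlier urine results, so clinicians' responses to positive urines could appear as an effect of engagement

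*Combined protocol and SAP*

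**What the plan says.** Section 2.2 sets one secondary aim: how provider and patient engagement with OARS bears on patients' opioid abstinence. Section 6.3 gives the analysis in three sentences.

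- **Population:** "The secondary analysis will use data from patients treated after OARS implementation".
- **Model:** a logistic regression to "estimate effect of provider and patient engagement with the OARS platform" on opioid-negative urine toxicology.
- **Exposure:** "number of days of OARS engagement, number of interactive features used". No time window relative to the urine test is given.
- **Outcome:** a negative urine. Which test or tests count, and when, is not stated.
- **Covariates:** demographics, other substance use, severity of opioid use and comorbidities. None is dated. Earlier urine results are not listed.

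Section 1.1 describes how the platform works. The list of MATRA inputs includes the patient's attendance and "levels of engagement in treatment", and ends with "and results of urine drug tests". It continues: "The resulting MATRA score is used by clinicians as a factor for considering early interventions and case management decisions". The software also "provides opportunities for patients to interact with their clinical providers".

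Section 5 keeps the medical record identifier to "link data across TAU and OARS conditions". Section 3.2 mentions time stamps in the OARS meta-data, under exploratory outcomes.

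**The concern.** The outcome of the regression is an input to the system whose use is the predictor. A positive urine can raise the risk score, the score can prompt clinician action, and that action may be recorded as further engagement. If engagement and urine results are then summarised over the same months, the coefficient partly measures clinicians reacting to positive tests.

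The sponsor could then conclude that provider engagement is unhelpful when it is only responsive, or miss a real benefit. If patients instead use the platform less after a positive test, patient engagement would look beneficial for the same reason. The plan's wording invites either coefficient to be read as an effect of OARS use.

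This is separate from unequal time in care. The bias remains when every patient is followed for the full eight months.

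**Working it through.** **The plan's own figure.** Section 4.1 gives a minimum of 200 patients to power the primary and secondary objectives. It cannot be re-derived, because no alpha, power, effect size, abstinence rate or intraclass correlation is given. The only available check is six clinics at the section 4.2 minimum: 6 × 35 = 210, which meets 200 but does not derive it.

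**Inputs from the documents.** 200 patients (section 4.1) and eight months under OARS per clinic (section 5).

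**Assumptions not in the documents.** One urine per month; a base of 2 provider days per month; the size of the feedback; patient risk varying with SD 1.5 on the logit scale.

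**Set-up 1.** True engagement effect zero.
- logit P(positive) = −0.8 + severity, so an average patient has P = 1/(1 + e^0.8) = 0.31.
- Provider days next month ~ Poisson(2 + k × previous result positive).
- Model: majority-negative status on total days over the period.

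With k = 0.5, an always-positive patient expects 8 × 2.5 = 20 days and an always-negative patient 8 × 2 = 16. The gap arises entirely from the urine results.

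| k (extra days) | OR for abstinence per 5 days | Rejection at 5% |
|---|---|---|
| 0 | – | about 5% |
| 0.5 | 0.56 | 93% |
| 1 | 0.38 | 100% |
| 2 | 0.24 | 100% |

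Repeat runs at k = 0.5 gave 88% to 90%, with odds ratios of 0.57 to 0.58.

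**Adding severity, as the plan would.** The table has no covariates. At k = 0.5, a severity measure correlated 0.5 with risk leaves rejection at 78% to 81%; at k = 1 and 2 it stays at 100%. Correlation 0.7 at k = 0.5 gives 66%. A perfect severity measure gives 16% at k = 0.5 and 52% at k = 1. With 400 runs, the Monte Carlo standard error near 80% is √(0.8 × 0.2/400) = 2 percentage points.

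**Set-up 2.** A different reading of the plan: last urine on total days, adjusted for severity (correlation 0.5), about 5 engagement days per month, 1,000 runs. Engagement changes by a rate ratio in the month after a positive urine.

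| Rate ratio | OR per SD of engagement | Rejection |
|---|---|---|
| 1.00 | 1.01 | 5.2% |
| 1.10 | 0.87 | 13% |
| 1.25 | 0.74 | 49% |
| 1.50 | 0.59 | 91% |
| 0.90 | 1.15 | 14% |
| 0.80 | 1.30 | 39% |
| 0.67 | 1.55 | 76% |

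The sign follows the direction of the feedback.

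**Time-ordered analysis.** Engagement is counted before the test and earlier results are adjusted for.
- Feedback from the last result only: rejection 4–8% in set-up 1 and 4.0–5.8% in set-up 2, with odds ratios about 1.00.
- Feedback from cumulative history: adjusting for the last result alone still rejects in 13–85% of runs; adding the running proportion positive restores 4–6%.
- Engagement also varying with latent severity by 10–20% per SD: last result plus severity rejects in 43–93% of runs; adding urine history lowers this only to 25–74%.

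**The case against.** **The last link is inferred.** Section 1.1 makes the score one factor that clinicians consider. Nothing says that the resulting action takes place inside OARS or counts as an engagement day or a feature used; a telephone call or extra visit might not. This stands. A reader might infer that abstinence demonstrably drives measured engagement. The documents show the route as far as clinician decisions and make the remainder plausible, because patient–provider interaction is a function of the software. They give no size.

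**A false benefit is less well supported.** The MATRA route concerns mainly provider engagement and points towards apparent harm. That patients use the platform less on relapse is not in the documents. This also stands, so no direction can be claimed for patient engagement.

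**The simulated models are readings of the plan.** Section 6.3 does not say that engagement and urine results are taken over the same months, and it does plan to adjust for severity. Better severity measurement shrinks the bias. However, it persisted with an imperfect measure under both readings, and section 6.3 contains nothing to exclude it. The repeated-measures wording there belongs to the OARS-versus-TAU hypotheses.

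**The remedy's near-nominal error rates are conditional.** They hold when engagement depends only on urine history that the model contains. Once engagement also tracks unmeasured severity, ordinary confounding remains.

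**Conclusion.** The concern holds in conditional form. If clinicians' responses to urine-informed scores add to counted OARS engagement, the section 6.3 analysis can report a spurious association that makes provider engagement look harmful or hides a benefit. Patient engagement could be biased in either direction.

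The size depends on assumption. With 0.5 or more extra provider days after a positive urine and a severity covariate correlated 0.5 with risk, false-positive rates were about 78% or more; stronger severity measurement lowers them. A 10% change in engagement, in either direction, more than doubled the nominal 5% in the second set-up. Test frequency, feedback size and the quality of the severity measure are not in the documents, so these figures are illustrative.

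A reader might go further and conclude that the secondary aim cannot be answered, or that OARS will be credited with a false benefit. The documents support neither: a better-ordered analysis is available, and the documented route points towards apparent harm. The OARS-versus-TAU comparison is not affected.

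**What to change.** Amend the secondary analysis in section 6.3 as follows.

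1. Make the urine test the unit of analysis and count engagement in the interval between the previous test and the current one.
2. Adjust for previous urine history: the last result and the running proportion positive. Use linked TAU results for the first OARS interval, with a new-patient indicator where there are none.
3. Keep the planned covariates, with substance use and severity measured before the exposure interval.
4. Use patient-clustered standard errors.
5. Enter provider and patient engagement as separate predictors.
6. Report an association, not an effect.

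**Cost.** Analysis wording and some programming. The record linkage in section 5 and the OARS time stamps in section 3.2 should supply the ordering. The sponsor should confirm that the time stamps cover the engagement measures, because they are described only for exploratory outcomes and no test frequency is given.

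**Downsides.** The estimate becomes a short-term, between-test association, which is a narrower question than engagement over the whole period. Patients with few tests contribute less. Residual confounding by unmeasured severity remains, so the change removes the feedback bias without guaranteeing an unbiased effect.

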7 HUMAN SUBJECTS PROTECTIONS

7.1 Institutional Review Boards

The study team will make efforts to minimize risks for participating clinics, providers, and patients. Study staff are responsible for assuring that this protocol is followed and the appropriate materials are provided to clinics at the time of enrollment. Any modifications to the protocol other study-related documents will be approved by the IRB prior to implementation.

7.2 Risk/Benefit Assessment

7.2.1 Risks

Because these research activities are limited to collection of data through the EHR and use of the OARS platform, this study poses minimal physical risks to participants. However, due to the highly stigmatized

nature of opioid use disorder and its treatment, the biggest factor leading to risk in any or all of these domains is loss of confidentiality (see below for a detailed description of safeguards to protect against loss of confidentiality).

7.2.2 Benefits

There may be no direct benefit to clinics, providers, or patients to participating in these research activities. There may be an indirect benefit to participants in the use of these data to inform quality improvement efforts surrounding the treatment of OUD in the primary care setting.

7.3 Informed Consent Process

The research team is requesting a waiver of consent for patient participants since this research involves no more than minimal risk and involves no procedures for which written consent is normally required outside of the research context. The risk of contacting patient participants and documenting their informed consent provides a possible risk of breach of confidentiality since there is no other need to contact patient participants. Therefore, this risk is determined to be greater than the risk of the study procedures. Additionally, informed consent would not be possible within this study design since the primary outcomes are meant to be evaluated with each clinic's entire patient population. Requiring informed consent may actually result in biased results since individuals who choose to consent (or not consent) may have a different probability of experiencing the outcomes of interest.

In addition, UCLA study staff will obtain verbal consent from provider participants who choose to participate in the semi-structured interview. The verbal consent process, and the interview that follows, will be conducted over a secure Zoom line to ensure participant confidentiality.

7.4 Participant Confidentiality

All study databases will be secured and encrypted with password-protected access systems. Any Q2i staff who have access to patient information will be members of the research study team, and as such, have completed relevant human subject research and HIPAA trainings.

In addition, a Certificate of Confidentiality will be acquired from the U.S. Department of Health and Human Services that will be applicable to this study. This certificate protects study staff from being compelled to disclose study-related information by any U.S. Federal, State, or local civil, criminal, administrative, legislative, or other proceedings. It thus serves to protect the identity and privacy of study participants.

7.5 Special Populations

Pregnant Women

Opioid use disorder affects pregnant women and many women may choose to receive treatment while pregnant. The collection of medical record data is of minimal risk to all patients receiving treatment for OUD including pregnant women. The understanding of the impact of providing medical care for the treatment of OUD in pregnant women presents an opportunity to understand, prevent, or alleviate a serious problem affecting the health or welfare of pregnant women or fetuses.

Children

We will exclude data related to minors treated for OUD from inclusion in the study database (both baseline and OARS).

Non-English speaking individuals

We will exclude non-English speaking providers and patients since participation is contingent on using the OARS platform (which is currently only available in English) once it is implemented. Therefore, non-English speaking providers and patients are not eligible to participate in the study.

Cognitively impaired individuals

Opioid use disorder is common in patients with psychiatric, organic, developmental, or other disorders that affect cognitive or emotional functions that may cause diminished capacity. The collection of medical record data is of minimal risk to all participants including those individuals who are cognitively impaired. The understanding of the impact of providing medical care for the treatment of OUD among those who are cognitively impaired presents an opportunity to understand, prevent, or alleviate a serious problem affecting the health or welfare in this patient population.

7.6 Compensation

Patients will not be compensated since no direct patient contact will be required and patients do not need to perform any study specific research activities.

For participating in the provider interviews, PCP participants can receive a total of \$150 compensation for completion of all research activities broken into the following segments:

- \$50 for completion of the first interview prior to OARS implementation
- \$50 for completion of second interview one month after OARS implementation
- \$50 for completion of third interview 6-8 months after OARS implementation

